1. LIST OF ABBREVIATIONS

AC	Attention Control
AE	Adverse Event
AIDS	Acquired Immune Deficiency Syndrome
ART	Antiretroviral Therapy
CBPM	Centers for Behavioral and Preventive Medicine
CDC	Centers for Disease Control and Prevention
CFAR	Center for AIDS Research
Co-I	Co-Investigator
CT	Chlamydia trachomatis
DSMC	Data Safety Monitoring Committee
Gc	Gonorrhea
HIPAA	Health Insurance Portability and Accountability Act
HIV	Human Immunodeficiency Virus
IRB	Institutional Review Board
MBSR	Mindfulness-Based Stress Reduction
MT	Mindfulness Training
NCCIH	National Center for Complementary and Integrative Health
NIH	National Institutes of Health
PCP	Primary Care Provider
PD	Project Director
PLWH	People living with HIV
PHI	Protected Health Information
PI	Principal Investigator
RCT	Randomized Clinical Trial
SAE	Serious Adverse Event
STI	Sexually Transmitted Infections
RA	Research Assistant
Trich	Trichomoniasis
TMH	The Miriam Hospital

2. BACKGROUND AND RATIONALE

2.1 Background

Based on estimates from the CDC, 1.2 million persons aged ≥ 13 years are living with HIV infection, while incidence rates of new infections reach 50,000 new cases per year.¹⁻⁴ In 2012, ~28,000 people were diagnosed with AIDS⁵ and ~14,000 people with an AIDS diagnosis died in 2011.⁵

CDC recommendations for people living with HIV (PLWH) include the adoption of safer sex practices and strict adherence to antiretroviral therapy (ART) when prescribed.⁶ Safer sex practices such as condom use with all partners and reduction in the number of partners, decrease the risk of contracting other sexually transmitted infections (STIs) and HIV super-infection, and reduce the likelihood of transmitting HIV to an uninfected partner. Adherence to ART improves viral suppression, reduces infectiousness and HIV-related morbidities, and increases longevity.⁷⁻⁹ Together, safer sex practices and ART adherence improve the health of PLWH and reduce the incidence of new HIV infections.¹⁰⁻¹⁷

Despite CDC recommendations, a significant proportion of PLWH still engage in risky sexual practices and show sub-optimal ART adherence to ART. For example, 26% to 35% of HIV-infected men who have sex with men report recent unprotected anal intercourse.^{18,19} Risky sexual behavior places the infected person at risk for other STIs and for HIV super-infection.²⁰ Unprotected sex also places partners at risk for HIV infection, fueling the epidemic. Likewise, only 30% of PLWH persons adhere to ART to the point of achieving viral suppression.^{21,22} Sub-optimal adherence to ART compromises individual health, increases health care costs, and can lead to the development of ART-resistant strains of HIV.^{9,23} Thus, poor adherence to CDC recommendations adversely affects both an individual's and the population's health.

Among the multiple barriers to adherence to CDC recommendations²⁴ patient-related factors such as stress, depression, and poor impulse control have been the most difficult to modify. PLWH are exposed to considerable stress due to poverty²⁵ and/or discrimination due to minority social status.²⁶⁻²⁹ Further, HIV remains highly stigmatized, further exacerbating stress levels. It is not surprising, given this stressful context, that many PLWH report elevated levels of depression.³⁰⁻³⁴ In the absence of strong coping skills, stress and depression can enhance impulsivity in vulnerable persons,³⁵ who then cope maladaptively (i.e., by using alcohol and other drugs, engaging in risky sex).³⁶⁻⁴⁶ Depression and stress have also been associated with poor ART adherence^{24,47-57} and risky sexual behavior.⁵⁸⁻⁶² Thus, stressful life circumstances, depression, and impulsivity conspire to undermine adherence to CDC recommendations.^{24,48,63-73}

2.2 Study Rationale

Mindfulness training can reduce perceived stress, depression, and impulsivity.

Mindfulness has been defined as the act of paying attention to the present moment's experience in an intentional and non-judgmental way.³⁶⁻³⁸ While mindfulness is a fundamental ability of the mind, studies have shown that mindfulness levels increase with training, thus showing that mindfulness is also a teachable skill.⁷⁴ The best known program is Mindfulness Based Stress Reduction (MBSR),⁷⁵ which offers training in traditional mindfulness meditation adapted to a non-Buddhist, clinical context. The MBSR program has been shown to be effective in reducing anxiety, depression, and a variety of physical symptoms in many medical conditions⁷⁶⁻⁷⁸ including cancer,⁷⁹⁻⁸² chronic pain,^{83,84} rheumatoid arthritis,⁸⁵ and fibromyalgia.⁸⁶

Current evidence suggests the efficacy of mindfulness training (MT) on the aforementioned barriers to adherence in the HIV context. First, MT improves depressive symptoms and perceived stress, with moderate to large effect sizes. Hofman et al.⁸⁷ reviewed 39 studies where

patients received MT for a range of psychiatric or medical conditions and reported that MT led to robust and sustained improvements in mood symptoms (Hedge's $g = 0.95$). The Campbell Collaboration⁸⁸ reviewed 31 RCTs, and found medium-sized post-intervention effects for depression ($g=0.54$) and for stress/distress ($g=0.56$). Goyal et al.⁸⁹ included 47 randomized clinical trials and found improvements in depression at 8 weeks that lasted up to 6 months. The most recent meta-analytic study⁹⁰ isolated results from 12 studies that included only participants diagnosed with a current episode of a depressive or anxiety disorder, and found significant benefits on depressive symptom severity for MT relative to controls.

[figure not shown]
Furthermore, by emphasizing the intentional and non-judgmental acceptance of any thought, feeling, or sensation arising in the field of consciousness, MT cultivates qualities that are the very opposite of impulsivity. Indeed, observational evidence suggests a possible effect of MT on impulsivity.⁹¹ Dispositional mindfulness (i.e., the capacity that individuals have to be mindful prior to training)^{92,93} has been associated with lower impulsivity and better self-control.⁹⁴ Higher dispositional mindfulness has been associated with reduced binge eating episodes and better sleep quality as well as with healthier dietary habits among students.^{95,96}

Prior studies among PLWH. Although mindfulness-based approaches are increasing used by PLWH,⁹⁷⁻⁹⁹ MT has not been well studied in the context of HIV. We found only 8 published studies¹⁰⁰⁻¹⁰⁷ and one unpublished study¹⁰⁸⁻¹¹⁰ of mindfulness-based interventions with PLWH. Our review, as well as previous reviews,^{111,112} suggests that MT reduces distress and promotes more adaptive coping in PLWH. The only study assessing the effect of MT on ART adherence did not show improvements; however, adherence was only a secondary outcome, only self-report measures of adherence were used, and low ART adherence was not an inclusion criterion.¹⁰⁴ No study has investigated the effect of MT on safer sex practices, and most studies suffer from methodological limitations (e.g., small samples, recruitment of low risk participants leading to possible ceiling effects on the outcomes). A particularly important limitation is that PLWH may have not received an adequate dose of MT due to low class attendance and high attrition in prior studies of group-based MT.^{103,107}

Conceptual model. Stress, depression, and impulsivity are associated with poor adherence to ART and risky sex among PLWH. Previous research with patients having various chronic illnesses, including HIV, shows that MT reduces distress and symptoms of depression. There is also observational evidence that MT may improve impulsivity. Building upon this empirical evidence as well as theories of mindfulness,^{113,114} we propose a model to guide the proposed R34 research and a future RCT. Figure 1 shows our expectation that a MT intervention will reduce stress, depressive symptoms, and impulsivity, which will improve safer sex practices and ART adherence. We will explore

these relationships in the proposed R34 research. For the future RCT, we will also investigate the longer-term hypotheses, i.e., that improved adherence to ART and safer sex will improve CD4 counts, reduce viral load, and reduce incident STIs. Key to these hypotheses is confirmation that patients receive an adequate dose of the MT intervention.

Rationale for the proposed research. The proposed research is needed (1) to adapt a previously developed phone-delivered mindfulness intervention to assure that it will deliver an adequate dose of MT for PLWH; (2) to refine the evaluation protocol; (3) to develop a comparison condition that controls for the time and attention patients receive in the MT intervention; and (4) to pilot-test the interventions and assessment protocols for feasibility and

acceptability. After this R34, we envision a R01-supported RCT to evaluate the efficacy of MT on adherence and safer sex among PLWH. This large RCT will advance the field and will have the following strengths: intervention mapping based on a conceptual model; provision of an adequate dose of MT; implementation of MT by skilled instructors following a detailed manual; separate instructors to avoid contamination across conditions; confirmation of intervention fidelity; measurement of psychological (e.g., depression), behavioral (e.g., ART adherence, risky sex), and biomedical (e.g., VL, STIs) outcomes; testing of hypothesized mediators and moderators; use of computerized assessments to minimize demand. These strengths will greatly enhance the quality of the research and permit stronger inferences to be drawn about the key hypotheses, namely: (1) MT will reduce perceived stress, depressive symptoms, and impulsivity, which (2) will improve ART adherence and increase safer sexual practices, which will in turn (3) improve CD4 counts and reduce VL, and (4) reduce the incidence of STIs. If effective, these hypothesized changes can also reduce HIV-related premature morbidity.

3. AIMS

This protocol seeks to satisfy Aim 4 of our R34 grant, namely:

Pilot test both interventions as well as the evaluation protocol for feasibility and acceptability (Study 4). PLWH ($n=50$) will be recruited and randomly assigned to MT ($n=25$) or to the control intervention ($n=25$), and assessed at baseline, post-intervention (3 months since baseline), and follow-up (5 months since baseline). The primary outcomes will be feasibility and acceptability. The secondary outcomes will include ART adherence and risky sex behaviors as well as possible mediators (i.e., depression, perceived stress, impulsivity) that will be included in full mediation analyses in the future RCT.

4. SAFETY ASSESSMENT

4.1. Overview

Overall, this is a low risk study. The attention control intervention and mindfulness training are low-risk, behavioral interventions. Thus, we anticipate that patients will incur minimal risks due to their participation in this study.

4.2. Protection Against Possible Risks

Possible risks during the study involve:

- a. Emotional discomfort during mindfulness practice
- b. Breach of confidentiality
- c. Minor side effects from venipuncture for assessments of viral load
- d. Depression and Suicidality

The level of risk for each of these events is minimal.

a. Emotional discomfort during mindfulness practice: Psychological distress during mindfulness practice is mild, of short duration, and rarely occurs in absence of ongoing serious psychiatric conditions; participants with suicidal ideation and ongoing psychosis will be excluded from participation in the study. In case a patient presents signs of severe psychological discomfort during or between sessions, he/she will be excused from participating in the mindfulness intervention. The mindfulness instructor will actively inquire at each phone session about psychological side effects that might occur during the session or during individual practice. Mindfulness instructors are experienced and trained on how to help individuals

presenting such issues. Participants will also be instructed to contact the Project Director (PD) should any discomfort arise during the training.

b. Breach of confidentiality: The likelihood of loss of privacy or confidentiality is rare and its impact on participants is likely to be minimal. Risks to privacy and confidentiality associated with this study will be described in the consent form along with our procedures to minimize this risk. Participant confidentiality will be maintained through a number of strategies. Each participant will be assigned a unique study identification number. The only individuals who will have access to participants' identifiers will be the PD, assessors, mindfulness instructors, and health educators. Mindfulness instructors and health educators must have access to participant identifiers in order to call the participants for their weekly sessions. Assessors will have access to participant identifiers in order to call the participants for their monthly pill counts. Assessors, mindfulness instructors, and health educators are all trained and experienced in following research protocols and participant confidentiality. Audio recordings of mindfulness and health education sessions will be reviewed promptly to ensure treatment fidelity and then destroyed. Checklists and paper records of the treatment fidelity review will not include identifying information but will be stored and handled using the same methods as with other paper data. Audio recordings of interviews will be summarized without participant identifiers and then destroyed following analysis.

Protection of study data will be assured by the use of locked files and password-protected computer databases with access available only to the study personnel. Biospecimens will be labeled only with the collection date and an anonymous numerical code; no identifiable patient information will be present on the samples. The PD will be responsible for collecting, handling and bringing the samples to the designated lab for analysis; no other personnel will have access to these samples.

c. Side effects from the venipuncture. Blood samples will be taken by venipuncture by IC phlebotomists. Venipuncture is a procedure commonly performed in general medical care which involves inserting a needle into a vein in the arm and withdrawing a sample of blood. Participants may experience mild discomfort associated with blood sample collection, including pain during blood drawing and subsequent bruising. In very rare circumstances participants may experience fainting or local infection. These risks will be minimized by having an experienced certified phlebotomist performing the venipuncture.

d. Depression and suicidality. Although participants with suicidality will be excluded from the study, depression is common among PLWH and suicidal ideation could emerge during the course of the study. The PD will calculate depression scores on the study questionnaire immediately after survey completion at each data collection point. If scores indicate that severe depressive symptoms are reported and/or if suicidal ideation is reported or if the PD has reason to be concerned about the welfare of the participant then the PD will follow the suicide protocol (Appendix 5). The PD, [name], a licensed mental health counselor; will either directly conduct an assessment of suicidality risk, or she will arrange for the PI, [name], a licensed psychologist, to conduct an assessment of suicidality risk. If neither of these persons are available, a licensed clinical psychologist who works full-time at the Immunology Center will be contacted to conduct an assessment of suicidality risk. If the licensed psychologist is not available other providers in the Clinic are likely to be available. If none of these options were available, the participant can be escorted to The Miriam Hospital Emergency Room.

A protocol for the assessment and management of suicidality risk is included in Appendix 5 of this application.

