4.5. Adverse Events and Serious Adverse Events

a. **Definition.** An adverse event (AE) is defined as any untoward medical occurrence in a participant temporally associated with participation in the clinical study. An adverse finding can include a sign, symptom, abnormal assessment (laboratory test value, vital signs, electrocardiogram finding, etc.) or any combination of these. A Serious Adverse Event (SAE) is any adverse event that results in one or more of the following outcomes:

- Death
- A life-threatening event
- Inpatient hospitalization or prolongation of existing hospitalization
- A persistent or significant disability/incapacity
- Important medical event based upon appropriate medical judgment

Note: A birth defect is a highly unlikely event considering our study intervention. This outcome has been excluded.

b. **Classification of AE Severity.** AEs will be labeled according to severity, which is based on their impact on the patient. An AE will be termed ‘mild’ if it does not have a major impact on the patient, ‘moderate’ if it causes the patient some minor inconvenience and ‘severe’ if it causes a substantial disruption to the patient’s wellbeing.

c. **AE Attribution Scale.** AEs will be categorized according to the likelihood that they are related to the study intervention. Specifically, they will be labeled either definitely, probably, possibly or unrelated to the study intervention. The determination of whether an AE is related to the study intervention will be made by the PD. If relatedness is unclear, the PD will seek the guidance of the PI.

Reportable and non-reportable events. The IRB at TMH requires reporting of all SAEs as well as of those AEs that are unanticipated and related to the study protocol or procedures (that is, they are “unlikely”, “possibly”, “probably” or “definitely” related). Unanticipated AEs are events, signs and symptoms that are not listed as risks on the consent form. Please note that AEs that are either anticipated or are “definitely not” related to the intervention procedures **are not reportable to the IRB at TMH.**

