4.6. AE Reporting Procedures and Follow-Up

All *reportable AEs* (see 4.5. for definition) will be reported by the PIs to the Institutional Review Board (IRB) at TMH. Serious adverse events (SAEs) are reported to the IRB within 24 hours as described below (“SAE reporting”). All other reportable adverse events will be reported during the routine annual continuation reports to the IRB. In addition, all AEs (reportable and non-reportable) will be provided to the Chair of the IMC prior to each IMC meeting and to the NCCIH program officer, annually.

All intervention visits (mindfulness and control sessions) and follow-up assessments will include proactive assessments of potential adverse events. The PD will record all AEs and SAEs in a secure database using the format in the example below:

Subject Identifier	AE Onset	AE End	AE Code	Severity	SAE? (y/n)	Relatedness	Action Taken	Outcome	Comments	
Subj001	11/1/15			1		2	1	1	Subject felt anxious during MT; resolved within 15 minutes	
Subj002										
Subj003	12/18/15			3		0	4	4	Subject fell while hiking; broke leg; withdrew from study	
Severity of AE: 1 = Mild 2 = Moderate 3 = Severe 4 = Life threatening or disabling		Relatedness to intervention: 0 = Definitely unrelated 1 = Unlikely 2 = Possibly related 3 = Probably related 4 = Definitely related			Action Taken: 0 = None 1 = Intervention modification 2 = Medical intervention (specify in comments) 3 = Hospitalization 4 = Intervention discontinued 5 = Other (specify in comments)			Outcome: 1 = Resolved 2 = Recovered with minor sequelae 3 = Recovered with major sequelae 4 = Continuing treatment 5 = Condition worsening 6 = Subject death		

Participants will be asked about all AEs at each intervention session and at each follow up assessment. AEs will be recorded on the AE log. The PD will report all AEs to the PIs as soon as possible. All AEs will be assessed to determine their classification and whether they meet criteria for an SAE. The PD will refer participants to their own physician for assistance with adverse symptoms. Each week the PIs will review AE reports from the previous week for events that were reported as new or continuing, and will follow all AEs to the point of a satisfactory resolution. The PIs will be available at all times to discuss other adverse symptoms with the PD and the study participants.

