- appears severely distressed during any in-person session (i.e., screening, baseline, or follow-up; as determined by recruiter judgment), or
- reports suicidal thoughts at any time to PD or Instructor, initiate a “distress check” to assess suicidality. This check must be conducted in a sensitive and caring way. For example, you can say to the participant the following: *“I would like to check in with you about how this experience was for you. I asked a lot of questions, and want to check in to ask how are you doing?”*

If participant says he/she is okay and does not meet any of the above criteria for enacting the suicide safety protocol, no further intervention will be taken.

However, if participant says she/he is upset, then the PD or Instructor will say: *“It is not uncommon for people to feel upset or emotional after answering questions like this (or, talking about experiences like this). We do ask many personal questions. It is also not uncommon for people to have thoughts of hurting themselves. Have you had thoughts of actually hurting yourself?”*

If participant has not had any thoughts of hurting herself and does not meet any of the criteria above for enacting the suicide safety protocol, then we will remind patients of the resources available for counseling within the Immunology Center. We will also give everyone a list of local agencies that provide counseling services, and say: *“You may find it helpful to contact one of these agencies to set up an appointment to talk to someone about the feelings that were raised today. Also, if you are ever in crisis or need to talk to someone immediately, you can call the Immunology Center.”*

If participant has had thoughts of hurting herself or meets any of the above criteria for enacting the suicide safety protocol, then we will start suicide safety protocol, described next.

Script to Screen for Suicidal Concerns

If suicidal thoughts or severe distress are reported at screening or during any intervention or assessment session, the PD or Instructor will start the suicide safety protocol.

The PD and Instructors will be trained to use the following script. If indicated (as outlined earlier), they will ask:

“I’d like to ask you a few additional questions, because I am concerned for your well-being and safety.

1. Have you ever attempted to harm yourself in the past?	NO	YES
2. Have you thought about how you might actually hurt yourself?	NO	YES → [How? _____]

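### Only mindfulness instructors are told to ask about psychological side effects at each session, so mild psychological events may be ascertained differently in the two arms

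*Combined protocol and SAP*

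**What the plan says.** Section 4.2 takes the study's risks one by one. Under item a, emotional discomfort during mindfulness practice, it says: "The mindfulness instructor will actively inquire at each phone session about psychological side effects". The sentence goes on to cover effects arising in the session and in home practice. Item d, on depression and suicidality, applies to everyone. It notes that "depression is common among PLWH and suicidal ideation could emerge during the course of the study" and provides that "The PD will calculate depression scores on the study questionnaire immediately after survey completion at each data collection point".

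Section 4.6 sets the general rule for both arms: "All intervention visits (mindfulness and control sessions) and follow-up assessments will include proactive assessments of potential adverse events". It repeats the requirement in other words: "Participants will be asked about all AEs at each intervention session and at each follow up assessment". The sample log in that section shows that brief, mild distress counts as an adverse event. Its first entry is a participant who felt anxious during mindfulness training and recovered within 15 minutes.

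Section 4.5 places attribution with the Project Director (PD): "The determination of whether an AE is related to the study intervention will be made by the PD". Section 7.6 lists the PD as not blinded.

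Appendix 5 starts the suicide safety protocol "If suicidal thoughts or severe distress are reported at screening or during any intervention or assessment session", in either arm.

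**The concern.** How often an event is recorded depends partly on how it is asked about. A prompt that names psychological discomfort, in the session and in home practice, can be expected to draw out more mild events than an inquiry that names no symptom. As written, that prompt belongs to one arm. Both arms are selected for distress (PHQ-4 of at least 2, section 5.3), so background psychological events are plausible among controls too.

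Two things are at stake. First, the adverse-event listings could show more psychological events under mindfulness for reasons of questioning alone, and mild distress in control participants could go unrecorded. Section 4.6 sets no stopping rules, and under section 4.4 the monitoring committee reassesses risk and benefit from lists classified by severity and relatedness. Second, section 3 makes piloting the evaluation protocol part of the aim, so an unequal adverse-event method could carry over into the planned larger trial.

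**Working it through.** The plan states no adverse-event rate or detection rate, so there is no figure to reproduce. The check is mainly a comparison of texts.

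**What each arm is asked at the weekly call**

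| Channel | Mindfulness | Control |
|---|---|---|
| All adverse events, proactively (4.6) | Every session | Every session |
| Named psychological inquiry covering session and home practice (4.2a) | Every session | Not stated |
| Adverse-event wording in the session outline (Appendices 1, 2) | None | None |
| Open discussion in the session outline | Last week's practice (from session 2) and participant feedback | Comments or questions on the material covered |

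**Whether the shared safeguards close the gap**

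- Depression scoring takes place at data collection points. Table 8.2 schedules these at baseline, post-intervention and follow-up, not at the eight weekly calls.
- The suicide protocol responds to suicidal thoughts, a PHQ-9 score of 15 or more, or severe distress. Mild, passing discomfort does not trigger it.
- Appendix 3 says pill-count callers will also ask how the participant has been feeling. These calls are monthly, serve both arms and are not described as adverse-event inquiries.
- The fidelity audit in section 7.5 covers essential intervention components on 10% of recordings. It does not mention adverse-event questions, so unequal questioning might not be noticed.

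Serious distress is therefore covered alike in both arms. What remains is mild or transient distress, which the section 4.6 log treats as recordable.

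**Illustration of size (all rates assumed)**

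Input from the documents: n = 25 per arm. Assumptions: the same true event proportion p in both arms, and detection s of 0.90 for mindfulness and 0.90, 0.75 or 0.50 for control.

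- Expected recorded events = n × p × s.
- Recorded ratio = s(mindfulness) / s(control), because n and p cancel.
- 95% half-width of the difference = 1.96 × √[a(1 − a)/25 + b(1 − b)/25], with a and b the recorded proportions p × s in the two arms.

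At p = 0.20:

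| Control detection | Mindfulness events | Control events | Ratio | Difference | Half-width |
|---|---|---|---|---|---|
| 0.90 | 25 × 0.20 × 0.90 = 4.5 | 4.5 | 1.0 | 0 | 0.21 |
| 0.75 | 4.5 | 25 × 0.20 × 0.75 = 3.75 | 1.2 | 0.03 | 0.21 |
| 0.50 | 4.5 | 25 × 0.20 × 0.50 = 2.5 | 1.8 | 0.08 | 0.19 |

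At p = 0.10 the counts with unequal detection are 2.25 against 1.88 or 1.25. At p = 0.40 they are 9.0 against 7.5 or 5.0. The ratios do not change. For unequal detection at these three values of p, the power of a two-sided 5% test (an assumed level; no such test is planned) to detect the artefact is 4% to 24%.

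The ratio only restates the assumed detection rates. The table shows what unequal questioning could do, not what it will do.

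**The case against.** The strongest reply is that section 4.6 already answers the point. It requires proactive assessment of all adverse events at every mindfulness and control session, and section 4.5 defines an adverse event broadly enough to include psychological symptoms. On this view item a of section 4.2 names the mindfulness instructor only because the hazard discussed there belongs to that arm, and it may simply be the mindfulness instance of the section 4.6 inquiry. The silence of the appendices is the same in both arms. Section 11.2 leaves data-collection detail to a manual of operations that is not part of these documents. Control instructors are clinical psychology residents with at least 5 years of experience (section 7.3) and are hardly likely to ignore distress.

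Much of this stands. A reader might infer that control participants get only a general question and that psychological events are therefore over-detected under mindfulness. The documents do not support either step. Section 4.6 asks for more than a general question, and if it is carried out with the same content in both arms, there is no asymmetry. A reader might also infer that a planned comparison would be biased. Section 12 plans no between-arm analysis of adverse events, and section 4.4 specifies no tabulation by arm for the committee.

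One part of the point survives. The only explicit psychological inquiry at sessions is written for one arm, and nothing in the documents makes the control inquiry equivalent.

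**Conclusion.** The point holds as a possibility, not as a demonstrated bias: mild or transient psychological events may be differentially ascertained, with mindfulness the arm more likely to show more of them. It rests on two readings that the documents leave open: that the inquiry in 4.2a goes beyond the one in 4.6, and that the control inquiry carries no equivalent psychological prompt.

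The size cannot be derived. The illustrative ratios of 1.0 to 1.8 depend wholly on assumed detection rates, and at an assumed 20% true rate the largest gap is 4.5 − 2.5 = 2 expected events. The reach is limited to descriptive adverse-event listings and the monitoring committee's review. Attribution by an unblinded PD could compound an imbalance there. The primary outcomes of feasibility and acceptability and the secondary efficacy outcomes are not touched. This is a minor point, worth acting on because the remedy is cheap.

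**What to change.** Amend sections 4.2a and 4.6 so that instructors in both arms use the same short scripted adverse-event inquiry at every session. It should include one psychological-discomfort prompt covering the session and home practice, in identical words for both arms. Place the script in Appendix 1 and Appendix 2.

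The extra attention to mindfulness practice has a legitimate safety purpose and need not be given up. If a mindfulness-specific probe is kept in addition, ask it after the common script, mark in the log which events came to light only through it, and report those separately.

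The cost is about a minute of call time per control session, or roughly 8 × 25 × 1 = 200 minutes over the trial if every control session is held. No change to the sample size, outcomes or analysis is needed.
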